**Table 3.7-1 Schedule of Assessments - Rollover Subjects from Trial 331-10-234**

| Assessment   | Screening/
Baseline

Last visit
from Trial
331-10-234/
Baseline for
Trial
331-10-236 | 24-Month Open-label Treatment Period |  |                          |  |                           |   |   | End of
Treatment | Follow-up
(clinic
visit not
required) b

21 ( $\pm$ 2)
days after
last dose
of IMP |
|--|--|--------------------------------------|--|--------------------------|--|---------------------------|---|---|---------------------|---|
|  |  | W1, 2, 4
( $\pm$ 3
days)       | M2, 3, 4
(monthly)
( $\pm$ 3 days) | M6
( $\pm$ 3
days) | M8, 10
(every
2 months)
( $\pm$ 3 days) | M12
( $\pm$ 3
days) | M15, 18,
21 (every
3 months
)
( $\pm$ 3 days) | M5, 7, 9,
11, 13, 14,
16, 17, 19,
20, 22, 23
( $\pm$ 3 days) a |                     |   |
| ECG  | X  | X W4
only                         |  | X                        |  | X                         | X M18
only   |   | X                   |   |
| Clinical laboratory tests
(hematology, serum
chemistry [including
prolactin, HbA1c and TSH],
and urinalysis) | X  | X W4
only                         |  | X                        |  | X                         | X M18
only   |   | X                   |   |
| Serum pregnancy test   | X  | X W4
only                         |  | X                        |  | X                         | X M18
only   |   | X                   |   |
| Urine pregnancy test   | X  | X c                       | X c                           | X                        | X c                                   | X                         | X c  |   |                     |   |
| Urine drug screen  | X  | X                                    | X  | X                        | X  | X                         | X   |   | X                   |   |
| Adverse events   | X  | X                                    | X  | X                        | X  | X                         | X   | X   | X                   | X   |
| Concomitant medications  | X  | X                                    | X  | X                        | X  | X                         | X   | X   | X                   | X   |
| Dispense investigational
product  | X  | X                                    | X  | X                        | X  | X                         | X   |   |                     |   |

BP = blood pressure; ET = early termination; M = month; W = week

aFollow-up contact may not be necessary if a subject who early terminated received the last dose of IMP > 21 ( $\pm$  2) days from the ET visit.bTelephone, Web, or other acceptable means of contact.c“Since Last Visit” version of the C-SSRS will be completed at each visit.dVital Signs – refers to pulse and heart rate interchangeably throughout the protocol.eIf the urine pregnancy test is positive, the result should be confirmed with a serum pregnancy test if a serum pregnancy test is not being performed during that visit. Additional urine pregnancy testing may be done at the discretion of the investigator.

**Table 3.7-2 Schedule of Assessments - De Novo Subjects**

| Assessment   | Screen         | Conversion Period a |                          | 24-Month Open-label Treatment Period |                          |                                    |                    |   |                     |  |   | End of Treatment d | Follow-up (clinic visit not required) e |
|--|----------------|--------------------------------|--------------------------|--------------------------------------|--------------------------|------------------------------------|--------------------|---|---------------------|--|---|-------------------------------|--|
|  |                | Base-line                      | W1, 2, 3 ( $\pm 3$ days) | Baseline (D1) b           | W1, 2, 4 ( $\pm 3$ days) | M2, 3, 4 (monthly) ( $\pm 3$ days) | M6 ( $\pm 3$ days) | M8, 10 (every 2 months) ( $\pm 3$ days) | M12 ( $\pm 3$ days) | M15, 18, 21 (every 3 months) ( $\pm 3$ days) | M5, 7, 9, 11, 13, 14, 16, 17, 19, 20, 22, 23 ( $\pm 3$ days) c |                               |  |
| Informed consent, demography, medical history, psychiatric history | X              |                                |                          |                                      |                          |                                    |                    |   |                     |  |   |                               |  |
| K-SADS-PL f   | X              |                                |                          |                                      |                          |                                    |                    |   |                     |  |   |                               |  |
| Prior medications  | X              |                                |                          | X                                    |                          |                                    |                    |   |                     |  |   |                               |  |
| Entrance criteria  | X              |                                |                          | X                                    |                          |                                    |                    |   |                     |  |   |                               |  |
| PANSS  | X              |                                |                          | X                                    | X
W4 only             | X                                  | X                  | X                                       | X                   | X M18 only                                   |   | X                             |  |
| CGI-S and CGI-I  | X g |                                |                          | X g                       | X
W4 only             | X                                  | X                  | X                                       | X                   | X M18 only                                   |   | X                             |  |
| CGAS   | X              |                                |                          | X                                    | X                        | X                                  | X                  | X                                       | X                   | X  |   | X                             |  |
| SAS, AIMS, & BARS  | X              |                                |                          | X                                    | X                        | X                                  | X                  | X                                       | X                   | X  |   | X                             |  |
| C-SSRS h  | X              | X                              | X                        | X                                    | X                        | X                                  | X                  | X                                       | X                   | X  |   | X                             |  |
| UKU and NY-AACENT  | X              |                                |                          | X                                    | X                        | X                                  | X                  | X                                       | X                   | X  |   | X                             |  |

**Table 3.7-2 Schedule of Assessments - De Novo Subjects**

| Assessment   | Screen | Conversion Period a |                          | 24-Month Open-label Treatment Period |                          |                                    |                    |   |                     |  |   | End of Treatment d | Follow-up (clinic visit not required) e |
|--|--------|--------------------------------|--------------------------|--------------------------------------|--------------------------|------------------------------------|--------------------|---|---------------------|--|---|-------------------------------|--|
|  |        | Base-line                      | W1, 2, 3 ( $\pm 3$ days) | Baseline (D1) b           | W1, 2, 4 ( $\pm 3$ days) | M2, 3, 4 (monthly) ( $\pm 3$ days) | M6 ( $\pm 3$ days) | M8, 10 (every 2 months) ( $\pm 3$ days) | M12 ( $\pm 3$ days) | M15, 18, 21 (every 3 months) ( $\pm 3$ days) | M5, 7, 9, 11, 13, 14, 16, 17, 19, 20, 22, 23 ( $\pm 3$ days) c |                               |  |
| Tanner staging   | X      |                                |                          |                                      |                          |                                    | X                  |   | X                   | X M18 only                                   |   | X                             |  |
| Physical examination   | X      |                                |                          |                                      |                          |                                    | X                  |   | X                   | X M18 only                                   |   | X                             |  |
| Body weight & waist circumference  | X      |                                | X                        | X                                    | X                        | X                                  | X                  | X                                       | X                   | X  |   | X                             |  |
| Height   | X      |                                |                          | X                                    |                          |                                    | X                  |   | X                   | X M18 only                                   |   | X                             |  |
| Vital signs (supine, sitting, & standing BP, pulse, and body temperature) i | X      |                                | X                        | X                                    | X                        | X                                  | X                  | X                                       | X                   | X  |   | X                             |  |
| ECG  | X      |                                |                          | X                                    | X W4 only                |                                    | X                  |   | X                   | X M18 only                                   |   | X                             |  |

**Table 3.7-2 Schedule of Assessments - De Novo Subjects**

| Assessment   | Screen | Conversion Period a |                          | 24-Month Open-label Treatment Period |                          |                                    |                    |   |                     |  |   | End of Treatment d | Follow-up (clinic visit not required) e |
|--|--------|--------------------------------|--------------------------|--------------------------------------|--------------------------|------------------------------------|--------------------|---|---------------------|--|---|-------------------------------|--|
|  |        | Base-line                      | W1, 2, 3 ( $\pm 3$ days) | Baseline (D1) b           | W1, 2, 4 ( $\pm 3$ days) | M2, 3, 4 (monthly) ( $\pm 3$ days) | M6 ( $\pm 3$ days) | M8, 10 (every 2 months) ( $\pm 3$ days) | M12 ( $\pm 3$ days) | M15, 18, 21 (every 3 months) ( $\pm 3$ days) | M5, 7, 9, 11, 13, 14, 16, 17, 19, 20, 22, 23 ( $\pm 3$ days) c |                               |  |
| Clinical laboratory tests (hematology, serum chemistry [including prolactin, HbA1c and TSH], and urinalysis) | X      |                                |                          | X                                    | X
W4 only             |                                    | X                  |   | X                   | X M18 only                                   |   | X                             |  |
| Serum pregnancy test   | X      |                                |                          | X                                    | X
W4 only             |                                    | X                  |   | X                   | X M18 only                                   |   | X                             |  |
| Urine pregnancy test   | X      |                                |                          | X                                    | X j           | X j                     | X                  | X j                          | X                   | X j                               |   |                               |  |
| Urine drug screen  | X      |                                | X                        | X                                    | X                        | X                                  | X                  | X                                       | X                   | X  |   | X                             |  |
| Adverse events   | X      | X                              | X                        | X                                    | X                        | X                                  | X                  | X                                       | X                   | X  | X   | X                             | X  |
| Concomitant medications  | X      | X                              | X                        | X                                    | X                        | X                                  | X                  | X                                       | X                   | X  | X   | X                             | X  |
| Dispense investigational product   |        | X                              | X                        | X                                    | X                        | X                                  | X                  | X                                       | X                   | X  |   |                               |  |

aThe conversion period lasts up to 4 weeks with a  $\pm$  3 day window for each weekly visit.

bFor subjects that participated in the conversion period, the baseline (Day 1) visit of the open-label treatment period will coincide with the end of the conversion period which is up to 4 weeks in duration.

cTelephone, Web, or other acceptable means of contact.

dIf a subject discontinues early before Month 24, either during the conversion period or the open-label treatment period, procedures noted for Month 24 must be completed at the ET visit.

eAll subjects (completers as well as premature withdrawals from either the conversion period or open-label treatment period) will be followed up either by telephone or other acceptable means of contact. Follow-up contact may not be necessary if a subject who early terminated received the last dose of IMP > 21 ( $\pm$  2) days from the ET visit.

fTo be completed only for de novo subjects who did not formerly participate in Trial 331-10-234.

gCGI-I **will not** be administered at screening or the baseline (Day 1) visit of the open-label treatment period.

hBaseline/Screening" version of the C-SSRS will be completed at screening and the "Since Last Visit" version will be completed at all other in-clinic visits.

iVital Signs – refers to pulse and heart rate interchangeably throughout the protocol.

jIf the urine pregnancy test is positive, the result should be confirmed with a serum pregnancy test if a serum pregnancy test is not being performed during that visit. Additional urine pregnancy testing may be done at the discretion of the investigator.

### **3.7.1 Schedule of Assessments**

#### **3.7.1.1 Screening and Baseline**

##### **3.7.1.1.1 Rollover Subjects**

Screening for rollover subjects occurs simultaneously with baseline at the end-of-treatment visit (Week 6) of Trial 331-10-234 (see [Table 3.7-1](#)). Rollover subjects entering from Trial 331-10-234 or their parent/legal guardian must sign the ICF for the open-label trial before any procedures specific to Trial 331-10-236 can be performed. Subjects will retain the same subject identification (Subject ID) number assigned in Trial 331-10-234. Screening/baseline values will be derived from the last visit of the double-blind phase 3 trial (ie, the Week 6 of Trial 331-10-234) for the following assessments: PANSS, CGI-S, CGI-I, CGAS, SAS, AIMS, BARS, C-SSRS, UKU, NY-AACENT, Tanner Staging Scale, physical examination, body weight, height, waist circumference, vital signs, ECG, clinical laboratory tests, urine drug screen, serum pregnancy test, and urine pregnancy test. The only additional procedures to be performed for rollover subjects at screening/baseline of the open-label trial are as follows:

- An assessment of all inclusion and exclusion criteria will be made to determine the subject's eligibility for the trial.
- Medical history from Trial 331-10-234 will be retained, but will be updated if necessary.
- Concomitant medications will be reviewed to assure that the subject is not receiving any prohibited medications.
- AE recording will begin with the signing of the ICF for Trial 331-10-236.
- The IMP will be dispensed to the subject.

##### **3.7.1.1.2 De Novo Subjects**

De novo subjects, whether or not they participated in Trial 331-10-234 must attend separate screening and baseline visits to allow for completion of eligibility assessments and washout of prohibited concomitant medications, if applicable.

###### **3.7.1.1.2.1 Screening**

For de novo subjects, the screening period begins after written informed consent and assent have been obtained and will take place between Day -28 and Day -1 prior to enrollment. Although the screening period continues up to administration of the first dose of IMP, screening procedures should be initiated with a sufficient amount of time allotted in order to obtain laboratory results and ECG results from the central reader prior

to the first dose. The sponsor reserves the right to utilize external quality oversight methods to ensure the validity of diagnosis, severity of illness, and other factors determining appropriateness of subject selection. After a subject has been told that a reliable informant may accompany the subject at all visits, the subject's parent/legal guardian has provided informed consent, and the subject has provided assent, a screening number will be provided. If a de novo subject previously participated in Trial 331-10-234, they will retain their subject identification number from Trial 331-10-234. Completion of screening activities may require more than 1 visit; however, only the initial visit will be registered. The screening period maximum of 28 days may be extended following approval by the medical monitor. Screening evaluations will include the following:

- Trial personnel will enter subject data into eSource to register all trial visits (initial screening visit only).
- An assessment of all inclusion and exclusion criteria will be made to determine the subject's eligibility for the trial.
- Demographic data will be recorded.
- Medical and psychiatric history will be recorded, including the DSM-5 diagnosis of schizophrenia that will be made by an adequately trained clinician.
- Previous medications taken within 30 days of screening will be recorded. Lifetime antipsychotic use will be recorded. Washout from prohibited concomitant medications will begin, if applicable (see [Table 4.1-1](#)).
- Diagnosis of schizophrenia will be confirmed by the K-SADS-PL, performed by an adequately trained rater (to be completed only for de novo subjects who did not formerly participate in Trial 331-10-234).
- A qualified and certified rater will administer the PANSS.
- A qualified rater will administer the CGI-S.
- A qualified rater will administer the CGAS.
- The investigator (or qualified designee) will complete the “Baseline/Screening” C-SSRS form.
- The investigator (or qualified designee) will administer the SAS, AIMS, and BARS.
- The investigator (or qualified designee) will administer the UKU and NY-AACENT.

- The investigator (or qualified designee) will complete Tanner Staging Scale assessment.

Note: The collection of Tanner Staging Scale data is required for this trial, and every attempt should be made to collect this information. Tanner Staging must be completed together with the physical exam in the most inconspicuous manner as possible for the subject. Tanner Staging could be completed by trial psychiatrist, trial-affiliated pediatrician, nurse-practitioner, or nurse (in case of countries or states where nurses are qualified to perform a complete physical examination). When Tanner Staging is not completed at a required visit, it should be collected at the next trial visit. A subject who reaches Stage 5 (both in pubic hair and genitalia) does not need to continue with Tanner Staging. Any psychiatrist who will perform the Tanner Staging evaluation will be trained and required to demonstrate inter-rater reliability before receiving certification to conduct the evaluation. A family practitioner or pediatrician who are investigators are considered trained and do not need to go through formal inter-rater reliability. Sites should make attempts to have examiners of both gender types. Attempts should be made to have examination performed by the same gender as the subject. Otherwise, a trial-affiliated personnel of the same gender (ie, nurse) as the subject should be in the same examination room as the subject.

- A physical examination will be performed.
- Body weight, height, and waist circumference will be recorded.
- Vital sign measurements (including blood pressure, pulse, and body temperature) will be recorded. Blood pressure and pulse are to be measured in the following order: supine, sitting, and standing after the subject has been in each position at least 3 minutes. See [Table 3.4.3.2-1](#) for exclusions based on outcome of screening vital sign measurements. Vital signs are to be completed before any blood is drawn.
- A standard 12-lead ECG will be performed after the subject has been supine and at rest for at least 5 minutes. Subjects with screening QT interval corrected for heart rate by Fridericia's formula (QTcF) or QT interval corrected for heart rate by the FDA Neuropharm Division formula (QTcN)  $\geq 450$  msec for males and  $\geq 470$  msec for females per the central reader's report will be excluded from the trial (see [Table 3.4.3.2-1](#) and [Section 3.7.3.4](#)). The ECG is to be completed before any blood is drawn.
- Blood samples will be collected for clinical laboratory tests, including hematology and serum chemistry (with prolactin, glycosylated hemoglobin [HbA1c], and thyroid-stimulating hormone [TSH and free thyroxine [T4]]). Blood will be drawn after a minimum 8-hour fast, if at all possible (see [Section 3.7.3.2](#)). See [Table 3.4.3.2-1](#) for exclusions based on outcome of screening clinical laboratory tests. Vital sign and ECG assessments should be completed before any blood samples are collected.
- A serum pregnancy test will be performed for all females. Subjects with a positive serum test result will be excluded from the trial.

- Urine will be collected from all potential subjects for urinalysis and urine screen(s) for drugs of abuse. See [Table 3.4.3.2-1](#) for exclusions based on outcome of urine drug screen(s). A urine pregnancy test will be performed for all females.
- AEs and concomitant medications will be recorded beginning with the signing of the ICF.

### **3.7.1.1.2.2 Conversion Period**

If the washout of prohibited medications prior to the baseline (Day 1) visit of the open-label treatment period is not appropriate for any de novo subject, in the opinion of the investigator, the subject must undergo cross-titration to oral brexpiprazole for 1 to 4 weeks during the conversion period, as described in [Section 3.2.2.1](#). Visits will occur at the end of each week during the conversion period. The goal of de novo subjects during the conversion period is to achieve a brexpiprazole monotherapy target starting dose of 1, 2, or 3 mg daily at any time after Week 1 per the investigator's discretion and to achieve the required washout of prohibited medications as per [Table 4.1-1](#). The subject will proceed to the baseline (Day 1) visit of the open-label treatment period once the target starting dose has been achieved and the required washout of prohibited medications has been completed.

All subjects will be assessed weekly at scheduled visits during the conversion period. The following evaluations will be performed at the baseline visit of the conversion period:

- The “Since Last Visit” version of the C-SSRS form will be completed.
- AEs and concomitant medications will be recorded.
- The IMP will be dispensed to the subject.

The following evaluations will be performed at each visit (ie, Week 1, 2, and 3):

- The “Since Last Visit” version of the C-SSRS form will be completed at Weeks 1, 2, and 3 visit.
- Body weight and waist circumference will be recorded.
- Vital sign measurements (including blood pressure, pulse, and body temperature) will be recorded. Blood pressure and pulse are to be measured in the following order: supine, sitting, and standing after the subject has been in each position at least 3 minutes. Vital signs are to be completed before any blood is drawn.

- Urine will be collected from all potential subjects for urinalysis and urine screen(s) for drugs of abuse.
- AEs and concomitant medications will be recorded.
- The IMP will be dispensed to the subject.

If a subject discontinues prematurely before the end of the conversion period, all procedures for the Month 24/ET visit must be completed at the ET visit.

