### **3.9 Screen Failures**

A screen failure subject is one from whom informed consent is obtained and is documented in writing (ie, subject signs an ICF), but who is not started on brexpiprazole treatment. For the purposes of this trial, treatment begins with the first dose of oral brexpiprazole during the conversion period or open-label treatment period.

Subjects who fail to qualify for the trial during screening for a reason other than a positive screen for drugs of abuse may be eligible to be rescreened one additional time at a later date. The medical monitor must be contacted before the rescreening of any de novo subject. In the event that a de novo subject is rescreened for trial participation, a

new ICF must be signed and a new screening number assigned. If a de novo subject previously participated in Trial 331-10-234, they will retain their subject identification number from Trial 331-10-234.

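### The visit at which converting de novo subjects start brexpiprazole schedules no weight, waist, vital signs or pregnancy test

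*Protocol*

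**What the plan says.** For de novo subjects who cross-titrate, Protocol Section 3.7.1.1.2.2 sets out two lists. The first opens with "The following evaluations will be performed at the baseline visit of the conversion period" and names the C-SSRS, adverse events with concomitant medications, and dispensing of IMP. The second, for conversion Weeks 1 to 3, adds weight, waist circumference, vital signs and urine collection.

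Table 3.7-2 matches the text. The rows "Body weight & waist circumference" and "Vital signs (supine, sitting, & standing BP, pulse, and body temperature" are marked at screening, at conversion Weeks 1 to 3 and at open-label Day 1, but are blank at conversion baseline. The row "Urine pregnancy test" and the serum test row are marked at screening and then not until open-label Day 1. Note b of that table says that, for converters, "the baseline (Day 1) visit of the open-label treatment period will coincide with the end of the conversion period".

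Table 3.2.2.1-1 starts brexpiprazole at 0.5 mg/day at conversion baseline, and Section 3.9 says that "treatment begins with the first dose of oral brexpiprazole during the conversion period or open-label treatment period".

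Screening lasts 3 to 28 days (Protocol 3.1). Section 3.7.1.1.2.1 adds "The screening period maximum of 28 days may be extended following approval by the medical monitor" and, among the screening procedures, "Washout from prohibited concomitant medications will begin, if applicable".

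SAP 7.1.2 takes the predose value on Day 1 of conversion as the conversion baseline and uses screening where that value is absent. SAP 8.2.3.2 and 8.2.4.2 analyse conversion-period weight, waist and vital signs in the same way as the open-label data, apart from z-scores.

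**The concern.** The schedule omits these measurements at the one visit where a converter goes from no brexpiprazole to brexpiprazole.

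**Baseline.** The SAP's first-choice baseline does not exist by design for weight, waist and vital signs, so its fallback becomes the normal case. Conversion-period changes, the 7% weight flags and the blood pressure and pulse flags that require a change from baseline are then measured from a point before the drug started. Other medication may be changing in that interval. The protocol itself singles out weight gain as a particular sensitivity in adolescents (Section 2.1).

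**Pregnancy.** A female converter can take her first dose on a result up to 28 days old, or older if screening is extended. Other routes into the trial are checked closer to dosing. A non-converting de novo subject needs a negative predose urine test on Day 1 (Section 3.7.1.1.2.3). A rollover subject is tested at the Week 6 visit of the parent trial, normally the day before her first open-label dose and up to about 7 days before if rollover is delayed. The protocol gives no reason for treating converters differently.

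**Working it through.** **Number of measures.** SAP 8.2.4.1 states 10 vital-sign parameters. Reproduced: temperature (1) + SBP, DBP and pulse in three positions (3 × 3) = 10. Adding weight and waist gives 10 + 2 = **12** measures whose change from baseline uses the screening value. Fewer have abnormality flags that depend on baseline: Protocol Appendix 1 and SAP Appendix 2 give no criterion for temperature or waist, which leaves 9 blood pressure and pulse parameters + weight = 10.

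**Time covered by a conversion-period change.** Inputs: s, days from the screening value to first dose, 3 to 28 (Protocol 3.1); w, nominal days on IMP at the visit. Days covered = s + w.

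| Visit | Days on IMP (w) | Days covered (s + w) |
|---|---|---|
| Conversion Week 1 | 7 | 10 to 35 |
| Conversion Week 3 | 21 | 24 to 49 |

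At Week 1, between 7/35 = 20% and 7/10 = 70% of the interval is on drug. A later predose value exists only if screening was spread over several visits or the site took an unscheduled one.

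**Effect on the 7% weight-gain flag.** The documents give no figure for weight drift between screening and first dose, so 1% and 2% in either direction are assumed. With screening weight 100, the flag is raised at 107. On-drug gain needed = 107 ÷ (weight at first dose) − 1.

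| Assumed weight at first dose | On-drug gain needed |
|---|---|
| 98 | 107/98 − 1 = 9.2% |
| 99 | 107/99 − 1 = 8.1% |
| 100 | 7.0% |
| 101 | 107/101 − 1 = 5.9% |
| 102 | 107/102 − 1 = 4.9% |

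**Pregnancy tests.** The last scheduled test before first dose is at screening, 3 to 28 days earlier. The next is at open-label Day 1, after a conversion of 7 to 28 days, or at the early-termination visit if the subject stops sooner.

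- Shortest interval between tests: 3 + 7 = 10 days.
- Longest: 28 + 28 = 56 days, or 59 with the 3-day visit window; longer still if screening is extended.
- For comparison, Month 12 (Day 372) to Month 15 (Day 465), from SAP Table 10.2-1: 465 − 372 = 93 days.

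The interval is therefore not unusual for this trial. What is missing is a test at the start of drug.

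**Does another rule supply the test?** Protocol 3.7.3.2 requires a result to be available before IMP, with no maximum age; the screening test satisfies that. The same section requires a negative urine test before Day 1 dosing. The protocol uses Day 1 for the open-label baseline visit, which converters reach after 1 to 4 weeks on IMP. If Day 1 were read as conversion Day 1, the schedule would omit a required test.

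**The case against.** **The baseline is already handled.** SAP 7.1.2 foresees a missing Day 1 value and names the substitute, which is pre-treatment. The analysis is descriptive. This stands: nothing is undefined, and the weakness is only that the baseline is older than it need be.

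**Background treatment is probably stable before the first dose.** Converters are subjects for whom prior washout was judged unsuitable. The recommended scheme in Table 3.2.2.1-1 leaves other antipsychotics unchanged until conversion Week 2 and reduces aripiprazole only from conversion baseline. The larger confounder, cross-titration after the first dose, would remain with a same-day baseline. This largely stands. Some other agents, such as CYP inhibitors, may still be washed out before the first dose, so the concern is reduced but not removed. The 28-day gap is also a permitted maximum and is not shown to be typical.

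**Flags are partly protected.** Blood pressure and pulse flags also need an absolute threshold, and the orthostatic criterion ignores baseline. This stands and limits the effect.

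**Pregnancy safeguards exist.** Screening includes both serum and urine tests. Sexually active subjects must agree to two contraceptive methods or abstinence, and the method is documented at each visit. IMP is withheld if pregnancy is suspected, and investigators may add tests. These lower the risk, but none of them is a scheduled test before first exposure.

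**Few subjects are affected.** SAP 8.1.2 expects a small number of converters, and SAP 10.7 drops conversion tables at 5 or fewer. This limits the effect on reporting. It does nothing for the individual subject given IMP on an old result.

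**Conclusion.** The concern holds. Text and table agree that the conversion-baseline visit schedules none of these assessments, although treatment starts there.

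The pregnancy test carries most of the weight: the last scheduled result is normally 3 to 28 days old at first dose, and 7 to 28 days on IMP follow before the next. This is a gap in the safety schedule and not a violation of the protocol's own rule.

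The baseline issue is minor. Twelve measures use a defined but older baseline in a small, descriptive part of the trial. The threshold range of 4.9% to 9.2% rests on an assumed drift of up to 2% and is illustrative. The documents do not give the number of converters. Open-label summaries use their own baseline, so the trial's main conclusions are barely affected. The change should still be made, because it is cheap and improves safety at first exposure.

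**What to change.** In Table 3.7-2 and Section 3.7.1.1.2.2, add to the conversion-baseline visit, before the first dose:

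- weight and waist circumference;
- supine, sitting and standing vital signs, with temperature;
- a urine pregnancy test for all females, which must be negative before dosing.

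SAP 7.1.2 then works as written and needs no change. For converters already treated, an optional footnote to the conversion tables can state that the baseline for these measures is the screening value. If no further converters will be enrolled, that footnote is the only part still open.

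The cost is a few routine measurements and one urine test at a visit that already takes place, for a small subset of subjects. The protocol edit is short, but it is an amendment and needs ethics committee approval under Section 13, so it is best combined with the next one.
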